4.3. Pharmacokinetic Evaluations

Etavopivat plasma concentrations will be summarized for each transfusion history stratum and overall with descriptive statistics by study visit, and planned collection time (e.g., pre-dose, 1-hour post-dose, etc..) and included in data listings. A line plot of semi-intensive PK concentration data by transfusion history stratum on both linear and semi-log scale will be provided for Day 1 and EOPT.

4.4. Safety Analyses

Safety analyses will be conducted using the Safety Set. Adverse event summaries, summaries of abnormal assessment results, and shift tables will include both primary and extension treatment periods.

4.4.1. Study Drug Exposure

Duration of study drug exposure will be calculated as the number of days with study drug, as determined below, and will be summarized by cohort and treatment period (Primary, Extension, and Overall) using descriptive statistics based on the following formula.

$$\begin{aligned} \text{Duration of Study Drug Exposure} \\ = (\text{Date of last dose in treatment period} \\ - \text{Date of first dose in treatment period}) + 1 \end{aligned}$$

Duration of study drug exposure for each patient will also be provided in a data listing.

4.4.1.1. Drug Exposure and Compliance

Duration of drug exposure will be summarized with descriptive statistics by transfusion history stratum and provided in a by-patient data listing.

Study drug compliance will be assessed by examination of the dispensed and returned tablets. Percent compliance will be calculated based on comparing the returned tablets to the expected number of tablets to be taken until treatment discontinuation per the following definition, where the number of tablets expected to be taken is defined as the duration of study drug exposure multiplied by 2:

$$\text{Percent Compliance} = \frac{(\text{Number of tablets dispensed} - \text{Number of tablets returned})}{(\text{Number of tablets expected to be taken})} \times 100$$

Study drug compliance will be summarized by transfusion history stratum and treatment period (Primary, Extension, and Overall) using descriptive statistics and will be categorized into the following categories: < 80%, 80-100%, > 100 – 120%, and > 120%. Percent compliance will be summarized with descriptive statistics overall and by transfusion history stratum.

The incidence of patients with early discontinuations (before W48D1 visit), dose holds, and dose reductions will be summarized with descriptive statistics.

A by-patient data listing will be presented. Patients who withdrew from the study early will be flagged.

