This study is a multicenter, open-label, Phase 2 study in adult patients with very low, low risk, or intermediate risk MDS per the International Prognostic Scoring System-Revised (IPSS-R) classification (see Appendix B).

The study will enroll up to 45 patients with MDS who will be evaluated for HI-E response composite derived from the MDS IWG 2018 criteria (modified by Platzbecker et al. 2019)

(see Appendix A). HI-E response assessment will be based on the individual patient's transfusion history in the 16 weeks prior to enrollment:

- NTD patients (received ≤ 2 RBC units for anemia within the prior 16 weeks): Hb increase of ≥ 1.5 g/dL over a continuous 8-week treatment period and no transfusion of RBC units for anemia over a continuous 8-week treatment period
 - Approximately 15 patients meeting the criteria for NTD may be enrolled in this study
- LTB patients (received 3 to 7 RBC units within the prior 16 weeks): No transfusion of RBC units for anemia over a continuous 8-week treatment period
 - Approximately 15 patients meeting the criteria for LTB may be enrolled in this study
- HTB patients (received ≥ 8 RBC units in the prior 16 weeks): ≥ 50% reduction in RBC units transfused over a continuous 8-week period.
 - Approximately 15 patients meeting the criteria for HTB may be enrolled in this study

Patients will be enrolled into a 48-week treatment period, including a 24-week Primary Treatment period and a 24-week Extension Treatment period. Patients demonstrating clinical benefit at the end of the 48-week treatment period may continue treatment. The dose of etavopivat is 400 mg once daily (QD) administered continuously; the selection of the starting dose is based on results from a Phase 1 study in patients with sickle cell disease (SCD) who were not receiving chronic RBC transfusions.

After the 6th patient completes a minimum of 4-weeks of daily etavopivat treatment, a safety review meeting will be held to confirm that the safety, exposure, and pharmacological response (PK/PD profile) are consistent with prior experience of etavopivat dosing in healthy volunteers and patients with sickle cell disease or thalassemia.

A futility assessment will be triggered when 15 patients across all strata or 8 patients in a single stratum reach 24 weeks of treatment, whichever occurs first. If both criteria are met at the same time, the overall futility assessment will be performed.

The futility criterion is defined as follows:

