6.0 STUDY INTERVENTION, CONCOMITANT THERAPY, AND PRECAUTIONS

6.1 Clinical Trial Material

Intervention Name	Etavopivat
Туре	drug
Dose Formulation	tablet
Unit Dose Strength	200 mg
Dosage Level	two tablets daily
Route of Administration	oral
Use	experimental
Sourcing	Sponsor
Appearance	film coated, oval-shaped tablets
Packaging and Labeling	blister pack

See the Study Pharmacy Manual for additional detail.

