7.1 Dose Modification / Discontinuation of Study Intervention

7.1.1 Adverse Event Interruption/Stopping Criteria

Criteria for treatment interruption, dose reduction, and treatment discontinuation due to AEs will be assessed at the investigator's discretion (see Section 8.7.6 and Section 8.7.7). Specific reporting criteria for liver enzyme abnormalities are provided in Section 8.7.2

Table 7-1 Suggested Dose Modifications for Treatment Related AEs

Severity	Non-Hematologic	Hematologic
Grade 3	Hold treatment until recovery to ≤ G1 or baseline, whichever is worse ^b , then resume at the next lower dose level (50% reduction). Contact Medical Monitoring if resumption of etavopivat at full dose is clinically indicated.	Continue treatment at the same dose. If dose interruption is clinically indicated, resume dosing at same dose level after recovery to \leq G2 or baseline, whichever is worse.
Grade 4	Permanently discontinue treatment ^c	Hold treatment until recovery to ≤ G2 or baseline, whichever is worse, then resume at the next lower dose level. Contact Medical Monitoring if resumption of etavopivat at full dose is clinically indicated.

a. In the event of Grade 3 nausea, vomiting, diarrhea, or rash, the patient can continue at the same dose if the patient is responsive to treatment measures within 72 hr.

b. A patient with a Grade 4 AE may resume treatment at the next lower dose level if the AE recovers to Grade 0-1 or baseline and if in the opinion of the Investigator and Sponsor, the patient can be monitored for recurrence of AE.

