9.7.3 Study Drug Compliance

Study drug compliance will be assessed by examination of the dispensed and returned pills. Percent compliance will be calculated based on comparing the returned pills to the expected number of pills to be taken between visits.

Study drug compliance will be summarized using descriptive statistics for each disease strata and overall.

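### Percent compliance assumes two tablets on every calendar day, so dose holds and 50% reductions read as missed doses, and taking too many tablets at a reduced dose can be masked

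*SAP*

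**What the plan says.** Percent compliance in SAP 4.4.1.1 is tablets dispensed minus tablets returned, divided by tablets expected, times 100. For the denominator, "the number of tablets expected to be taken is defined as the duration of study drug exposure multiplied by 2". Results are summarised by transfusion stratum and by treatment period (Primary, Extension, Overall), and grouped as below 80%, 80 to 100%, above 100 to 120%, and above 120%.

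SAP 4.4.1 introduces the duration with the words "Duration of study drug exposure will be calculated as the number of days with study drug". Its formula is the last dose date minus the "Date of first dose in treatment period", plus 1. Neither formula has a term for held days or for a reduced dose.

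In the protocol, the full dose is 400 mg once daily (1.1 Synopsis), given as "two tablets daily" of 200 mg (6.1). Table 7-1 (7.1.1) suggests holding treatment for certain related events. For a Grade 3 non-hematologic event the patient should "then resume at the next lower dose level (50% reduction"). Section 7.1.2 lets a reduced dose be taken from supply already dispensed, permits a return to the original dose after at least 14 tolerated days, and withdraws patients whose interruption for a related event exceeds 28 days. Section 9.7.3 describes compliance as "comparing the returned pills to the expected number of pills to be taken between visits".

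**The concern.** A compliance percentage should compare what the patient took with what the patient was told to take. Here the denominator stays at the full-dose count whatever was prescribed, which produces two errors in opposite directions.

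- A patient whose dose was held or halved, and who followed that instruction, appears to have missed tablets. With a long enough modification the patient lands in the below-80% category.
- A patient told to take one tablet who keeps taking two can appear fully compliant. The above-120% category, where such use ought to show, does not pick it up.

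Both errors fall on patients with tolerability problems. Dose interruptions and reductions are a secondary endpoint kept in this SAP (1.1.1.2), so the compliance table would sit beside that endpoint and describe the same events as poor adherence.

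**Working it through.** **Inputs.** Tablet strength 200 mg, two daily (protocol 6.1). Full dose 400 mg daily (protocol 1.1). Reduction 50% (Table 7-1). Period length 24 weeks (protocol 1.1), so 24 × 7 = 168 days for illustration. I assume that every tablet not taken is returned and that any hold lies between the first and last dose of the period.

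**The plan's multiplier.** 400/200 = 2 tablets a day, so the factor of 2 is right at full dose. At the reduced level it is 200/200 = 1.

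**Patient who follows instructions.** Let D be the days from first to last dose inclusive, h the held days and r the days at half dose. Tablets taken = 2(D − h − r) + r = 2D − 2h − r. The SAP result is

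C = 100 × (2D − 2h − r) / 2D = 100 × (1 − h/D − r/2D).

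With D = 168, so 336 tablets expected:

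| Held days | Half-dose days | Tablets taken | SAP compliance |
|---|---|---|---|
| 0 | 14 | 322 | 95.8% |
| 14 | 14 | 294 | 87.5% |
| 28 | 0 | 280 | 83.3% |
| 0 | 84 | 252 | 75.0% |
| 28 | 84 | 196 | 58.3% |
| 0 | 168 | 168 | 50.0% |

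Measured against prescribed tablets, every row is 100%.

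**When the below-80% category is reached.** This needs h/D + r/2D > 0.20. With D = 168, that is r > 67.2 with no hold (68 days or more at half dose), or h > 33.6 with no reduction (34 held days or more). Because a single interruption over 28 days for a related event leads to withdrawal, 34 held days would take more than one such hold, or a hold for another reason. One 28-day hold alone gives a score below 80% only if D is under 140 days.

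**Patient who takes two tablets while prescribed one.** Tablets taken = 2(D − h); tablets prescribed = 2(D − h) − r.

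- h = 0, r = 84: the SAP gives 336/336 = 100.0%; on prescribed tablets 336/252 = 133.3%.
- h = 28, r = 112: the SAP gives 280/336 = 83.3%; on prescribed tablets 280/168 = 166.7%.

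Both belong above 120%. The SAP rule places both in 80 to 100%.

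**Weight of one patient.** With about 15 patients planned per stratum, one misplaced patient moves a category by 1/15 = 6.7 percentage points. Actual stratum sizes are not given.

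**The case against.** The strongest reply is that little depends on this figure. Compliance is descriptive, no efficacy analysis uses it, and the Per-Protocol Set has been dropped (SAP 5.2). Adverse event rates use their own time-on-study formula (SAP 4.4.2). SAP 4.4.1.1 also reports the incidence of holds, reductions and early discontinuations with a by-patient listing, and SAP 4.4.2 tabulates events requiring dose modification. Short modifications barely move the score, and a single 28-day hold in 168 days leaves the patient in the 80 to 100% category. All of this stands and limits the consequence. None of it corrects the percentage.

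A reader might infer more than the documents support in four ways.

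- *That over-use at a reduced dose always scores 100%.* It does so only when no hold falls in the same summary period. Reductions under Table 7-1 follow a hold, so a lower score is common on that pathway unless the hold fell in the other treatment period.
- *That overdoses would go unreported.* Overdose is reported within 24 hours through Special Situation Reports (protocol 6.5 and 8.7.11); percent compliance is not the means of detecting it.
- *That the exposure summary is wrong.* The sentence in full reads "Duration of study drug exposure will be calculated as the number of days with study drug, as determined below", which makes the formula the definition. What remains is a mismatch between label and formula.
- *That the SAP contradicts protocol 9.7.3.* That section does not say whether the expected number follows the planned or the currently prescribed dose. The SAP fills a gap, in a way that gives poor answers here.

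Table 7-1 is also headed as suggested modifications, applied at the investigator's discretion, so these changes are permitted by the protocol rather than required by it.

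**Conclusion.** The concern holds for the compliance denominator. As written, the rule gives a wrong percentage for any patient with a hold or reduction inside the period who follows instructions, and nothing elsewhere in the two documents corrects it. The error ranges from a few points for brief changes to 50 points for a whole period at half dose. Over-use at a reduced dose can be hidden in the 80 to 100% category.

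The damage is confined to the descriptive compliance summary and its categories. The examples rest on a 168-day period and complete tablet return. The documents do not say how many patients had holds or reductions, so the effect on the reported tables cannot be computed. A hold that runs into permanent discontinuation does no harm, because the span ends at the last dose taken.

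If the duration were read as its introductory words suggest, with held days removed, the hold part of the error would disappear and the reduced-dose part would remain.

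**What to change.** In SAP 4.4.1.1, define expected tablets as the sum, over the days from first to last dose in the period, of the tablets prescribed on that day: the full-dose number at full dose, the reduced number after a documented reduction, and zero on documented held days. If the sponsor also wants tablets taken against two per day, report it separately as relative dose intensity.

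In SAP 4.4.1, either label the last-minus-first-plus-1 figure as treatment duration, or subtract held days so that the formula matches its description.

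The cost is a short wording change and a small amount of programming, with no change to any clinical rule. It depends on the eCRF holding start and stop dates for holds and reductions. The protocol records the action taken for each adverse event (8.7.8.1) and asks for the rationale and instructions for a dose change to be documented when it is made before a clinic visit (7.1.2). It does not show that these dates are captured, so that should be confirmed first. If they are not, the compliance table should carry a footnote saying that it is calculated against full dose and flag patients with modifications.

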4.4.2. Adverse Events

All AEs will be coded using version 26.1 of MedDRA and will be displayed in tables and data listings using SOC and PT.

Adverse events will be summarized in tables presenting both number and percent of patients as well as number of events and incidence rates (events per 100 patient-years). For the former, a patient is counted once for a given SOC and PT. For the latter, each individual adverse event will be counted separately.

For ongoing patients or patients who have discontinued treatment within 28 days prior to the analysis date, time on study is calculated as (data cut date – date of first dose + 1)/365.25. For patients who have discontinued treatment, time on study is calculated as (date of last dose + 28 – date of first dose + 1)/365.25. Cumulative patient-years are the sum of time on study for all patients in the specified group (e.g. NTD).

Analyses of adverse events will be performed for those events that are considered treatment-emergent, which is defined as any adverse event that emerges or worsens in the period from first dose of study drug to 28 days after the last dose of study drug.

TEAEs will be summarized by SOC and PT by transfusion history stratum and overall for the following categories, unless otherwise noted:

- All TEAEs
- Drug-related TEAEs
- Grade 3 or higher TEAEs

- Grade 3 or higher drug-related TEAEs
- TEAEs leading to study drug discontinuation
- Serious TEAEs
- Serious drug-related TEAEs
- TEAEs requiring dose modification (any dose reduction from 400 mg or temporary interruption in dosing due to an adverse event)

TEAEs will be considered drug-related if assessed by the Investigator as possibly related or related, or if relationship is missing. For summaries of severity, when reporting number and percent of patients, only the maximum severity level will be presented in the severity summaries.

All adverse events occurring on-study will be listed in patient data listings. By-patient listings also will be provided for the following: SAEs, and AEs leading to discontinuation of study drug.

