4.3 Treatment and Study Duration

4.3.1 Treatment Duration

Duration of study treatment will be 48 weeks, including 24 weeks in the Primary Treatment period, and 24 weeks in the Extension Treatment period.

Duration of study for an individual patient may last up to 58 weeks and includes a Screening Period (up to 6 weeks before study treatment), the treatment period of the study for up to 48 weeks, and a Safety Follow-up visit at 28 days (+ 7 days) after last dose of study drug. Study duration in patients who continue etavopivat treatment due to clinical benefit will be > 58 weeks.

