7.2.2 Study Withdrawal

Patients may voluntarily withdraw from the study at any time for any reason without prejudice.

Patients may withdraw or be withdrawn from the study for any of the following reasons:

- Death
- Lost to follow-up
- Termination of study by Sponsor
- Withdrawal of consent

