8.7.5 Procedures for Recording and Reporting Adverse Events and Serious Adverse Events

Any AE or SAE that occurs from time of the first dose of study drug through 28 days after the last dose of study drug should be recorded on the AE eCRF. Only SAEs that occur from the time of consent until first dose of study drug that are considered to be related to a protocol-mandated procedure need to be reported as an SAE. All other AEs and SAEs from time of consent until first dose of study drug should be reported as medical history.

In order to avoid vague, ambiguous, or colloquial expressions, the AE should be recorded in standard medical terminology rather than the patient's own words. Whenever possible, the Investigator should combine signs and symptoms that constitute a single disease entity or syndrome into a final diagnosis, if appropriate. For example, fever, cough, and shortness of breath may be reported as pneumonia, if that is the final diagnosis. Each AE is to be evaluated for duration, severity, seriousness, and causal relationship to the investigational drug. The action taken and the outcome must also be recorded.

Serious Adverse Events: SAEs that occur during Screening and are related to a protocol-mandated procedure or SAEs that occur from first dose to within 28 days after last dose of study drug, whether or not related to study drug, must be reported to Novo Nordisk Global Safety within 24 hours of knowledge of the event (see Page 4). After the 28-day reporting window, only SAEs assessed as related to study drug need to be reported. All SAEs, regardless of relationship to study drug, must be reported using the Novo Nordisk SAE Report Form. It is important that the Investigator provides an assessment of relationship of the SAE to study treatment at the time of the initial report. The contact information for reporting of SAEs can be found on the Novo Nordisk SAE Report Form itself and is also provided on Page 4.

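### Patient-years for adverse event rates do not stop at death, withdrawal of consent or loss to follow-up, so rates are understated whenever a patient leaves observation early

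*SAP*

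**What the plan says.** SAP 4.4.2 presents adverse events in two ways: as the number and percent of patients, and as "number of events and incidence rates (events per 100 patient-years"), with each event counted separately. The denominator is a simple sum: "Cumulative patient-years are the sum of time on study for all patients in the specified group".

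Two rules define time on study.

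- Ongoing patients are counted to the data cut. So are recent stoppers: "patients who have discontinued treatment within 28 days prior to the analysis date, time on study is calculated as (data cut date" less the date of first dose, plus one day), divided by 365.25.
- All other discontinued patients: "For patients who have discontinued treatment, time on study is calculated as (date of last dose + 28" days, less the date of first dose, plus one day), divided by 365.25.

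The numerator uses the same window. A treatment-emergent event is one that "emerges or worsens in the period from first dose of study drug to 28 days after the last dose of study drug". Collection matches it in Protocol 8.7.5: "Any AE or SAE that occurs from time of the first dose of study drug through 28 days after the last dose".

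Observation can end before that window closes. Protocol 7.2.2 begins its list with "Patients may withdraw or be withdrawn from the study for any of the following reasons" and names death, loss to follow-up, termination by the sponsor and withdrawal of consent. Protocol 8.7.2.1 also provides for deaths within 28 days of the last dose.

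Neither rule stops at any of these events. Nothing elsewhere in the SAP supplies a cap, including 3.9 (Missing Data) and 4.1.1 (Patient Disposition).

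**The concern.** In a rate of events over person-time, the denominator should contain only time in which an event could occur and be recorded. After death no event can occur. After withdrawal of consent or loss to follow-up, an event may occur but will not be recorded. The SAP formula still credits such a patient with time up to last dose + 28 days, or up to the data cut.

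The error has one direction. It can enlarge the denominator but never shrink it, and nothing in the numerator offsets it. The patients involved include those who die soon after their last dose, whose safety data matter most. Because the SAP supports an abbreviated report with a final safety update after early termination (SAP 1.1), these rates are among its main safety outputs.

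**Working it through.** The documents give no patient-years and no adverse event rate, so there is no stated figure to reproduce. The check compares the SAP formula with the same formula stopped at the end of observation.

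**Inputs from the documents**
- Credit after last dose: 28 days (SAP 4.4.2).
- Planned treatment: "Duration of study treatment will be 48 weeks, including 24 weeks in the Primary Treatment period, and 24 weeks in the Extension Treatment period" (Protocol 4.3.1), which is 336 days in all, with 168 days in the primary period.
- Planned sample size: 45, about 15 per stratum (SAP 1.2.1).

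**Assumed, not in the documents**
- f, the fraction of patients whose observation ends within 28 days of last dose: 10% and 20%.
- d, days from last dose to the end of observation: 0 (worst case) and 14.
- E, days from first to last dose, counting both: 336, 168 and 84. The shortest value allows for early termination.

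**One affected patient under the last dose + 28 rule**
- SAP person-days: E + 28.
- Observed person-days: E + d.
- Excess: 28 − d, so at most 28 days, or 28/365.25 = 0.077 patient-years.

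**Group**
- Overstatement of patient-years = (E + 28) / [(E + 28) − f(28 − d)] − 1.
- Worst case at E = 168, f = 10%, d = 0: 196 / (196 − 2.8) − 1 = 1.4%.
- Worst case at E = 168, f = 20%, d = 0: 196 / (196 − 5.6) − 1 = 2.9%.

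| E (days) | f = 10%, d = 0 | f = 20%, d = 0 | f = 10%, d = 14 | f = 20%, d = 14 |
|---|---|---|---|---|
| 336 | 0.8% | 1.6% | 0.4% | 0.8% |
| 168 | 1.4% | 2.9% | 0.7% | 1.4% |
| 84 | 2.6% | 5.3% | 1.3% | 2.6% |

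With f = 0 every entry is zero.

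**In absolute terms**, with 45 patients, E = 168, f = 10% and d = 0:
- SAP: 45 × 196 / 365.25 = 24.15 patient-years.
- Stopped at exit: (45 × 196 − 4.5 × 28) / 365.25 = 23.80 patient-years.
- A reported rate of 100 per 100 patient-years would become 24.15/23.80 × 100, which is 101.4 before rounding (101.5 from the rounded values).

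**The data-cut rule** has the same gap. A patient who stopped within 28 days before the analysis date and then died or withdrew is counted to the cut, not to the exit.

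**The case against.** The strongest defence is that the 28 days are deliberate and, for most patients, right. They match the treatment-emergent window, the collection period and the safety follow-up visit 28 days after last dose. Protocol 7.0 separates stopping treatment from leaving the study: patients who stop are encouraged to stay in safety follow-up. Entry is limited to very low, low or intermediate IPSS-R risk. So few patients may leave inside the window, and the documents do not say how many do. All of this stands. It limits the size of the error, but it does not supply the missing stop.

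A reader might infer several stronger things that the documents do not support.

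- *That every discontinued patient receives the full 28 days.* Those who stopped within 28 days before the analysis date are counted only to the data cut.
- *That all the rates are necessarily too low.* They are too low only if at least one patient contributing to the denominator leaves observation early.
- *That the bias differs between transfusion strata.* It would if early exits cluster in one stratum, but nothing in either document shows that they do.
- *That the distortion is large because one patient's time can be multiplied.* A patient who dies on Day 20, dosed to that day, is credited with 48 days against 20, or 2.4 times. But the SAP sums time over the group. With 45 patients at 168 days each, one such excess is 28 / (45 × 196) = 0.3% of the total.

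It is also fair to say that the consequence is limited. The study has a single arm, and no safety test or safety decision rule uses these rates. The number and percent of patients with each event do not depend on patient-years. Discontinuation reasons are tabulated (SAP 4.1.1), early withdrawals are flagged (SAP 4.4.1.1) and all on-study events are listed (SAP 4.4.2).

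**Conclusion.** The point holds as a conditional defect in a stated formula. SAP 4.4.2 does not end time on study at death, withdrawal of consent or loss to follow-up, so for any patient who leaves observation before the credited period ends the denominator is too large and the event rate too low.

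The group effect is probably a few percent or less: about 0.4% to 5.3% over the tabulated assumptions, and nil if everyone is observed to the end of the window. The upper figures require 20% of patients to leave on the very day of last dose after only 84 days of treatment. The fraction leaving, the timing of exit and the exposure are all assumed. This is a minor correction to a descriptive rate and does not touch the efficacy analysis.

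**What to change.** In SAP 4.4.2, change both rules so that time on study ends at the earliest of:

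- last dose + 28 days;
- death;
- withdrawal of consent, or last contact if lost to follow-up;
- data cut.

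The cost is one line of text and one line of programming. The dates should already be available: deaths in the reporting period are reported as serious events (Protocol 8.7.2.1), and study discontinuations with reasons come from the End of Study form (SAP 4.1.1). No new data are needed, and patients observed for the whole window keep the same time on study. It would also help to report how many patients left observation within 28 days of last dose, so that a reader can see whether the correction mattered.
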